Appendix 14: Study Details Specific to RO7247669 2100 mg+ Tira Arm (Cohorts 1 and 2)

A14-6 SCHEDULES OF ACTIVITIES AND SAMPLE COLLECTION FOR RO7247669 2100 mg+TIRA ARM (COHORT 1)

Table A14-5 Schedule of Activities for RO7247669 2100 mg+Tira Arm (Cohort 1)

Assessment/Procedure ^a	Protocol Section	Screening (see Appendix 10)	Treatment Cycles (21-Day Cycles)		Pre-Surgery	Surgery CLND	Post-Surgery	Treatment Comp./ Discon. ^b	Long- Term Follow- Up	Surgery Follow-Up ^c	
			Cycle 1	Cycle 2							
		D –28 to D –1	D1 (≤7D after randomization)	D1 (+ 1D)	Wk 6 (≤8D to surgery)	Wk 7 (± 7D)	Wk 10 (≥20D after surgery)	Wk 13	Every 3M (±7D)	6M after surgery (±7D)	
IMP Administration											
RO7247669 administration (2100 mg)	A14-4.1.2		x	x							
Tiragolumab administration			x	x							
Clinical Assessments											
Molecular profile of melanoma	4.5.2		Whenever updated information becomes available								
Weight ^d	4.5.3		x	x	x		x	x		x	
Complete physical examination								x			
Limited physical examination ^d	4.5.4 and A14-4.1.2		x	x	x		x			x	
Vital signs			x	x	x		x	x		x	
12-Lead ECG ^d	4.5.5		x	x				x			
TTE or MUGA scan	4.5.6							x			

Appendix 14: Study Details Specific to RO7247669 2100 mg+ Tira Arm (Cohorts 1 and 2)

Table A14-5 SCHEDULE OF ACTIVITIES FOR RO7247669 2100 mg+TIRA ARM (COHORT 1) (cont.)

Assessment/ Procedure ^a	Protocol Section	Screening (see Appendix 10)	Treatment Cycles (21-Day Cycles)		Pre-Surgery	Surgery CLND	Post-Surgery	Treatment Comp./ Discon. ^b	Long- Term Follow- Up	Surgery Follow-Up ^c
			Cycle 1	Cycle 2						
			D –28 to D –1	D1 (≤ 7D after randomization)	D1 (+ 1D)	Wk 6 (≤ 8D to surgery)	Wk 7 (± 7D)	Wk 10 (≥ 20D after surgery)	Wk 13	Every 3M (± 7D)
Clinical Assessments (cont.)										
ECOG Performance Status ^d	Appendix 6			X	X	X		X	X	X
Surgery (CLND)	3.1.5, Appendix 4						X			
Tumor response assessments	4.5.7					X				As clinically indicated
Disease status assessments	4.5.7.2				X			X ^e	X	
Concomitant medications	A14–4.2		X	X	X		X	X		
Adverse events ^f	5.3.1, 5.5.1, and 5.6		X	X	X		X ^f	X ^f	X ^f	X ^f
Clavien-Dindo assessment	4.5.8 and Appendix 5							X		X
Follow-up and anti-cancer treatment	4.6.1								X ^g	
Local Laboratory Assessments										
Hematology	4.5.9.1		X ^h	X ^h	X		X	X		X
Chemistry			X ^h	X ^h	X ⁱ		X	X		X

Appendix 14: Study Details Specific to RO7247669 2100 mg+ Tira Arm (Cohorts 1 and 2)

Table A14-5 SCHEDULE OF ACTIVITIES FOR RO7247669 2100 mg+ TIRA ARM (COHORT 1) (cont.)

Assessment/ Procedure ^a	Protocol Section	Screening (see Appendix 10)	Treatment Cycles (21-Day Cycles)		Pre-Surgery	Surgery CLND	Post-Surgery	Treatment Comp./ Discon. ^b	Long- Term Follow- Up	Surgery Follow-Up ^c
			Cycle 1	Cycle 2						
			D –28 to D –1	D1 (≤ 7D after randomization)	D1 (+ 1D)	Wk 6 (≤ 8D to surgery)	Wk 7 (± 7D)	Wk 10 (≥ 20D after surgery)	Wk 13	Every 3M (± 7D)
Local Laboratory Assessments (cont.)										
Lipid panel	4.5.9.1				x			x		
Coagulation (INR and aPTT)			x ^h	x ^h	x					
TSH, free T3 (or total T3), free T4			x ^h		x		x	x		x
Cardiac enzymes			x ^h	x ^h	x ^j			x		
C-reactive protein			x ^h	x ^h	x		x	x		x
Pregnancy test			x ^h	x ^h	x		x	x		x ^k
Urinalysis			Perform as clinically indicated.					x		
Central Laboratory Assessments										
Serum autoantibody sample	4.5.9.2		Perform if a patient experiences a suspected immune-mediated adverse event. Autoantibody analysis should be repeated for patients who develop signs or symptoms suggestive of autoimmune disease (e.g., lupus erythematosus).							
PK samples			Refer to Section A14–7.							
ADA samples			Refer to Section A14–7.							

Appendix 14: Study Details Specific to RO7247669 2100 mg+ Tira Arm (Cohorts 1 and 2)

Table A14-5 SCHEDULE OF ACTIVITIES FOR RO7247669 2100 mg+TIRA ARM (COHORT 1) (cont.)

Assessment/ Procedure ^a	Protocol Section	Screening (see Appendix 10)	Treatment Cycles (21-Day Cycles)		Pre-Surgery	Surgery CLND	Post-Surgery	Treatment Comp./ Discon. ^b	Long- Term Follow- Up	Surgery Follow-Up ^c
			Cycle 1	Cycle 2						
			D –28 to D –1	D1 (≤7D after randomization)	D1 (+ 1D)	Wk 6 (≤8D to surgery)	Wk 7 (± 7D)	Wk 10 (≥20D after surgery)	Wk 13	Every 3M (±7D)
Central Laboratory Assessments (cont.)										
Blood and plasma samples for biomarkers	4.5.9.2		Refer to Section A14–7.							x (only if onsite)
Pre-dose tumor biopsy				x ^d						Refer to Section A14–7.
Resected tissue						x				
Tumor biopsy (optional)	4.5.11		Perform at the time of unacceptable toxicity, loss of clinical benefit, relapse, or at any other time if deemed clinically feasible by the investigator.							

ADA=anti-drug antibody; CLND=complete lymph node dissection; Comp.=completion; CT=computed tomography; D=day; Discon.=discontinuation; ECOG=Eastern Cooperative Oncology Group; IMP=investigational medicinal product; M=month; MUGA=multiple-gated acquisition; PK=pharmacokinetic; T3=triiodothyronine; T4=thyroxine; TSH=thyroid-stimulating hormone; TTE=transthoracic echocardiogram; Wk=week.

Note: On treatment days, all assessments and procedures should be performed prior to dosing, unless otherwise specified.

^a If a visit is precluded because of a holiday, vacation, or other circumstance, it can occur outside of the specified window.

^b Regardless of whether they complete the study drug treatment period or discontinue study drug prematurely, patients who proceed to surgery will return to the clinic for a treatment completion/discontinuation visit 6 weeks after surgery and patients who do not proceed to surgery will return to the clinic for a treatment completion/discontinuation visit not more than 30 days after the final dose of study treatment.

^c Patients who proceed to surgery will have the surgery follow-up 6 months after surgery.

^d Assessment may be performed within 24 hours prior to dosing during the treatment period.

^e The disease status assessments at Week 13 should include a mandatory CT scan.

Appendix 14: Study Details Specific to RO7247669 2100 mg + Tira Arm (Cohorts 1 and 2)

Table A14-5 SCHEDULE OF ACTIVITIES FOR RO7247669 2100 mg + TIRA ARM (COHORT 1) (cont.)

^f After initiation of study treatment, all adverse events will be reported until 30 days after the final dose of study treatment or until initiation of new systemic anti-cancer therapy, whichever occurs first, and serious adverse events and adverse events of special interest will continue to be reported until 135 days after the final dose of study treatment or until initiation of new systemic anti-cancer therapy, whichever occurs first. After this period, all deaths, regardless of cause, should be reported. In addition, the Sponsor should be notified if the investigator becomes aware of any serious adverse event that is believed to be related to prior exposure to study treatment (see Section 5.6). *For details on reporting all treatment-related non-serious adverse events that lead to surgical delay, see Section 5.6.* The investigator should follow each adverse event until the event has resolved to baseline grade or better, the event is assessed as stable by the investigator, the patient is lost to follow-up, or the patient withdraws consent. Every effort should be made to follow all serious adverse events considered to be related to study treatment or trial-related procedures until a final outcome can be reported.

^g Patients who complete the treatment period, regardless of whether they complete the study drug treatment period or discontinue study drug prematurely, patients who proceed to surgery will have their first long-term follow-up visit 3 months after surgery and patients who do not proceed to surgery will have their first long-term follow-up visit 3 months after the final dose of study treatment. Information on survival follow-up and new anti-cancer therapy (including targeted therapy and immunotherapy) will be collected via telephone calls, patient medical records, and/or clinic visits approximately every 3 months until death (unless the patient withdraws consent or the Sponsor terminates the study). If a patient requests to be withdrawn from follow-up, this request must be documented in the source documents and signed by the investigator. If a patient withdraws from the study, the study staff may use a public information source (e.g., county records) to obtain information about survival status only. For an experimental arm in which all patients discontinued treatment and passed the safety follow-up window, as well as approximately 80% of patients discontinued the study, the Sponsor may conclude the arm (the remaining ~20% of patients will be discontinued from the study).

^h Laboratory tests must be performed within 72 hours prior to dosing during the treatment period. If screening laboratory assessments were performed within 72 hours prior to Day 1 of Cycle 1, they do not have to be repeated.

ⁱ At the pre-surgery visit, adrenocorticotropic hormone, cortisol, S100, and erythrocyte sedimentation rate will be included in the chemistry panel.

^j This is only applicable if elevated levels of cardiac enzymes were detected in previous assessments.

^k If periods are missed or delayed before the 6-month follow-up visit, pregnancy testing should be repeated. This test can be performed by a local gynecologist.

^l The Cycle 2 Day 1 on-treatment tissue sample must be collected up to 72 hours prior to drug administration.

Appendix 14: Study Details Specific to RO7247669 2100 mg+ Tira Arm (Cohorts 1 and 2)

A14-7 SCHEDULE OF PHARMACOKINETIC, IMMUNOGENICITY, AND BIOMARKER SAMPLES FOR RO7247669 2100 mg+ TIRA ARM (COHORT 1)

Visit	Time	Sample Type
Day 1 of Cycle 1	Prior to first infusion (-6 hr to 0 hr)	
 • RO7247669 PK (serum) • RO7247669 ADA (serum) • Tiragolumab PK (serum) • Tiragolumab ADA (serum) • Biomarkers (blood, plasma)
	30 (\pm 10) minutes after the end of tiragolumab infusion	
 • Tiragolumab PK (serum)
	30 (\pm 10) minutes after the end of RO7247669 infusion	
 • RO7247669 PK (serum)
Day 1 of Cycle 2	Prior to infusion (-6 hr to 0 hr)	
 • RO7247669 PK (serum) • RO7247669 ADA (serum) • Tiragolumab PK (serum) • Tiragolumab ADA (serum) • Biomarkers (blood, plasma)
	30 (\pm 10) minutes after the end of RO7247669 infusion	
 • RO7247669 PK (serum)
Surgery CLND Week 7	Prior to surgery (-24 hr to 0 hr)	
 • RO7247669 PK (serum) • RO7247669 ADA (serum) • Biomarkers (blood, plasma)
Post-surgery Week 10 ^a	At visit	
 • RO7247669 PK (serum) • RO7247669 ADA (serum) • Biomarkers (blood, plasma)
Treatment completion/ discontinuation Week 13	At visit	
 • RO7247669 ADA (serum) • RO7247669 PK (serum) • Biomarkers (blood, plasma)
Long-term follow-up Every 3 months (\pm 7 days) ^b	At visit ^b	
 • Biomarkers (blood, plasma)
Surgery follow-up 6 months after surgery (\pm 7 days)	At visit	
 • RO7247669 ADA (serum) • RO7247669 PK (serum) • Biomarkers (blood, plasma)

ADA=anti-drug antibody; CLND=complete lymph node dissection; PK=pharmacokinetic; Tira=tiragolumab.

Note: On the basis of emerging safety or efficacy data, the number of PK and ADA samples may be reduced or sample collection may cease altogether. Additionally, collected samples may not be analyzed if not warranted. On the basis of emerging biomarker data, the number of biomarker samples may be reduced or sample collection may cease altogether.

^a Week 10 biomarker samples must be obtained \geq 20 days post-surgery.

^b To be collected if visit is conducted on site.

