Appendix 13: Study Details Specific to Atezo + Tira Arm

Table A13-7 SCHEDULE OF PHARMACOKINETIC, IMMUNOGENICITY, AND BIOMARKER SAMPLES FOR ATEZO + TIRA ARM (cont.)

Visit	Time	Sample Type
Long-term follow-up Every 3 months (\pm 7 days) ^b	At visit	
• Biomarkers (blood, plasma)
Surgery follow-up 6 months after surgery (\pm 7 days)	At visit	
• Atezolizumab PK (serum)• Atezolizumab ADA (serum)• Tiragolumab PK (serum)• Tiragolumab ADA (serum)• Biomarkers (blood, plasma)

ADA=anti-drug antibody; Atezo =atezolizumab; CLND=complete lymph node dissection; PK=pharmacokinetic; Tira =tiragolumab.

Note: On the basis of emerging safety or efficacy data, the number of PK and ADA samples may be reduced or sample collection may cease altogether. Additionally, collected samples may not be analyzed if not warranted. On the basis of emerging biomarker data, the number of biomarker samples may be reduced or sample collection may cease altogether.

^a Week 10 biomarker samples must be obtained \geq 20 days post-surgery.

^b To be collected if visit is conducted on site.

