Appendix 14: Study Details Specific to RO7247669 2100 mg+Tira Arm (Cohorts 1 and 2)

A14-4 MATERIALS AND METHODS SPECIFIC TO RO7247669 2100 mg +TIRA ARM

A14-4.1 TREATMENT IN RO7247669 2100 mg+TIRA ARM

A14-4.1.1 Formulation, Packaging, and Handling

A14-4.1.1.1 RO7247669

The RO7247669 drug product will be supplied by the Sponsor as a 50 mg/mL concentrate for solution for infusion.

For information on the formulation, packaging, and handling of RO7247669, refer to the pharmacy manual and the RO7247669 Investigator's Brochure.

A14-4.1.1.2 Tiragolumab

The tiragolumab drug product will be supplied by the Sponsor as a 60 mg/mL concentrate for solution for infusion.

For information on the formulation, packaging, and handling of tiragolumab, refer to the pharmacy manual and the Tiragolumab Investigator's Brochure.

A14-4.1.2 Dosage, Administration, and Compliance

Patients in the RO7247669 plus tiragolumab (RO7247669+Tira 2100 mg) arm will receive treatment as outlined in [Table A14-1](#). Patients in Cohort 1 will receive treatment for 2 cycles (6 weeks) until surgery, or until unacceptable toxicity or loss of clinical benefit, whichever occurs first (see [Section 3.1.2](#) for details).

Patients in Cohort 2 will receive treatment until unacceptable toxicity or loss of clinical benefit as determined by the investigator after an integrated assessment of radiographic and biochemical data, local biopsy results (if available), and clinical status (e.g., symptomatic deterioration such as pain secondary to disease) (see [Section 3.1.2](#) for details). It is recommended that treatment be initiated no later than 7 days after randomization (Cohort 1) or enrollment (Cohort 2).

Table A14-1 Treatment Regimen for RO7247669 2100 mg+Tira Arm

Cycle Length	Dose, Route, and Regimen (drugs listed in order of administration)
21 days	
• RO7247669 2100 mg IV on Day 1 of each cycle ^a• Tiragolumab 600 mg IV on Day 1 of each cycle

Tira = tiragolumab.

^a After the safety run-in has been completed, the Sponsor may explore lower doses (e.g., 1200 mg and 600 mg).

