Appendix 14: Study Details Specific to RO7247669 2100 mg+ Tira Arm (Cohorts 1 and 2)

A14-9 SCHEDULE OF PHARMACOKINETIC, IMMUNOGENICITY, AND BIOMARKER SAMPLES FOR RO7247669 2100 mg+TIRA ARM (COHORT 2) (cont.)

Visit	Time	Sample Type
Day 1 of Cycles 8, 12, and 16	Prior to infusion (–6 hr to 0 hr)	
• Tiragolumab PK (serum)• Tiragolumab ADA (serum)• RO7247669 PK (serum)• RO7247669 ADA (serum)• Biomarkers (blood, plasma)
Treatment discontinuation visit (≤30 days after last dose)	At visit	
• RO7247669 PK (serum)• RO7247669 ADA (serum)• Biomarkers (blood, plasma)

ADA=anti-drug antibody; CLND=complete lymph node dissection; PK=pharmacokinetic; Tira=tiragolumab.

Note: On the basis of emerging safety or efficacy data, the number of PK and ADA samples may be reduced or sample collection may cease altogether. Additionally, collected samples may not be analyzed if not warranted. On the basis of emerging biomarker data, the number of biomarker samples may be reduced or sample collection may cease altogether.

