Appendix 16: Study Details Specific to RO7247669 600 mg +Tira Arm

A16-7 SCHEDULE OF PHARMACOKINETIC, IMMUNOGENICITY, AND BIOMARKER SAMPLES FOR RO7247669 600 mg+TIRA ARM

Visit	Time	Sample Type
Day 1 of Cycle 1	Prior to first infusion (-6 hr to 0 hr)	
 • RO7247669 PK (serum) • RO7247669 ADA (serum) • Tiragolumab PK (serum) • Tiragolumab ADA (serum) • Biomarkers (blood, plasma)
	30 (\pm 10) minutes after the end of tiragolumab infusion	
 • Tiragolumab PK (serum)
	30 (\pm 10) minutes after the end of RO7247669 infusion	
 • RO7247669 PK (serum)
Day 1 of Cycle 2	Prior to infusion (-6 hr to 0 hr)	
 • RO7247669 PK (serum) • RO7247669 ADA (serum) • Tiragolumab PK (serum) • Tiragolumab ADA (serum) • Biomarkers (blood, plasma)
	30 (\pm 10) minutes after the end of RO7247669 infusion	
 • RO7247669 PK (serum)
Surgery CLND Week 7	Prior to surgery (-24 hr to 0 hr)	
 • RO7247669 PK (serum) • RO7247669 ADA (serum) • Tiragolumab PK (serum) • Tiragolumab ADA (serum) • Biomarkers (blood, plasma)
Post-surgery Week 10 ^a	At visit	
 • RO7247669 PK (serum) • RO7247669 ADA (serum) • Tiragolumab PK (serum) • Tiragolumab ADA (serum) • Biomarkers (blood, plasma)
Treatment completion/ discontinuation Week 13	At visit	
 • RO7247669 ADA (serum) • RO7247669 PK (serum) • Tiragolumab PK (serum) • Tiragolumab ADA (serum) • Biomarkers (blood, plasma)
Long-term follow-up Every 3 months (\pm 7 days) ^b	At visit ^b	
 • Biomarkers (blood, plasma)

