Appendix 16: Study Details Specific to RO7247669 600 mg +Tira Arm

A16-7 SCHEDULE OF PHARMACOKINETIC, IMMUNOGENICITY, AND BIOMARKER SAMPLES FOR RO7247669 600 mg+TIRA ARM (CONT'D)

Visit	Time	Sample Type
Surgery follow-up 6 months after surgery (± 7 days)	At visit	
• RO7247669 ADA (serum)• RO7247669 PK (serum)• Biomarkers (blood, plasma)

ADA = anti-drug antibody; CLND = complete lymph node dissection; PK = pharmacokinetic; Tira = tiragolumab.

Note: On the basis of emerging safety or efficacy data, the number of PK and ADA samples may be reduced or sample collection may cease altogether. Additionally, collected samples may not be analyzed if not warranted. On the basis of emerging biomarker data, the number of biomarker samples may be reduced or sample collection may cease altogether.

^a Week 10 biomarker samples must be obtained ≥ 20 days post-surgery.

^b To be collected if visit is conducted on site.

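### A14-7 takes no tiragolumab PK or ADA sample after the second dose, unlike A13-7 and A16-7, so tiragolumab ADA in that arm can be under-counted and is not comparable across arms

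*Combined protocol and SAP*

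**What the plan says.** Tiragolumab dosing is the same in both RO7247669 combinations. Table A14-1 gives "Tiragolumab 600 mg IV on Day 1 of each cycle", and A14-4.1.2 limits Cohort 1 to two cycles. Table A16-1 has the same tiragolumab dose and timing.

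The sampling schedules differ:

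- **A14-7 (2100 mg + Tira, Cohort 1).** Tiragolumab PK and ADA are drawn before dosing on Cycle 1 Day 1 and Cycle 2 Day 1, with one further PK sample after the Cycle 1 infusion. Weeks 7 and 10 list "RO7247669 PK (serum) • RO7247669 ADA (serum) • Biomarkers (blood, plasma". Week 13 and the visit 6 months after surgery list "RO7247669 ADA (serum) • RO7247669 PK (serum) • Biomarkers (blood, plasma".
- **A16-7 (600 mg + Tira).** Tiragolumab PK and ADA continue at Weeks 7 and 10, and Week 13 reads "RO7247669 ADA (serum) • RO7247669 PK (serum) • Tiragolumab PK (serum) • Tiragolumab ADA (serum) • Biomarkers (blood, plasma". The 6-month row drops tiragolumab: "RO7247669 ADA (serum)• RO7247669 PK (serum)• Biomarkers (blood, plasma".
- **A13-7 (Atezo + Tira).** Tiragolumab PK and ADA are taken at Weeks 7, 10 and 13 and again 6 months after surgery: "Tiragolumab PK (serum)• Tiragolumab ADA (serum)• Biomarkers (blood, plasma".
- **A14-9 (2100 mg + Tira, Cohort 2).** Tiragolumab PK and ADA are taken before dosing at Cycles 1 to 4, 8, 12 and 16. The row headed "Treatment discontinuation visit (≤30 days after last dose" has RO7247669 assays and biomarkers but no tiragolumab assay.

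**The concern.** The proportion of patients found ADA-positive depends on how many samples are taken after exposure and when. An arm with one early sample cannot be set beside arms with four or five samples spread over months unless the table is cut back to the time point they share.

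The pair most affected is 2100 mg + Tira and 600 mg + Tira. They contain the same two drugs, with tiragolumab at the same dose, and differ in the RO7247669 dose. That is the natural comparison for judging whether the RO7247669 dose changes tiragolumab immunogenicity or exposure. Under A14-7 one side of it has no tiragolumab measurement after dose 2, and none near surgery, when the tumour specimen is resected.

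The difference looks unintended. A14-2.6 describes the combination as not yet tested clinically, whereas A16-2.6 says it is being tested in this study, so A16 appears to be the later text. The later schedule contains the three visits that A14-7 lacks.

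**Working it through.** The plan states no figure to reproduce here. The check sets the schedules side by side.

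**Step 1. Planned tiragolumab samples**

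| Visit | A14-7 (2100 mg + Tira, Cohort 1) | A16-7 (600 mg + Tira) | A13-7 (Atezo + Tira) |
|---|---|---|---|
| Cycle 1 Day 1, pre-dose | PK, ADA | PK, ADA | PK, ADA |
| Cycle 1 Day 1, after tiragolumab infusion | PK | PK | PK |
| Cycle 2 Day 1, pre-dose | PK, ADA | PK, ADA | PK, ADA |
| Week 7 (surgery) | none | PK, ADA | PK, ADA |
| Week 10 | none | PK, ADA | PK, ADA |
| Week 13 | none | PK, ADA | PK, ADA |
| 6 months after surgery | none | none | PK, ADA |
| **Post-baseline ADA samples** | **1** | **4** | **5** |
| **PK samples in total** | **3** | **6** | **7** |

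Cohort 2 under A14-9 has post-baseline tiragolumab ADA at Cycles 2, 3, 4, 8, 12 and 16, which is up to 6 while the patient stays on treatment.

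**Step 2. Timing against the second dose**

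Cycle c Day 1 falls on day 1 + 21 × (c − 1). Cycle 2 Day 1 is therefore day 22, and the draw precedes that day's infusion. Week 13 covers days 85 to 91, so A16-7 and A13-7 follow tiragolumab for 85 − 22 = 63 to 91 − 22 = 69 days after dose 2, on nominal dates. A14-7 follows it for 0 days.

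In Cohort 2, Cycle 4 Day 1 is day 64 and Cycle 8 Day 1 is day 148. A patient who stops between them has a last tiragolumab sample on day 64 (Week 10), because the discontinuation visit has none.

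**Step 3. Direction**

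Let p be the cumulative proportion who would be found ADA-positive under the longer schedule, and f the share of those first detectable after day 22. A14-7 detects p × (1 − f). This equals p only if f = 0 and is otherwise lower. The direction is fixed, but the amount is not.

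**Step 4. Scale, by assumption only**

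Neither p nor f is in the documents. A13-3.2, A14-3.2 and A16-3.2 call tiragolumab ADA rare in Study GO30103 without a rate. Taking f from 25% to 75%:

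- p = 2%: detected 2% × 0.75 = 1.5% down to 2% × 0.25 = 0.5%.
- p = 5%: detected 5% × 0.75 = 3.75% down to 5% × 0.25 = 1.25%.

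For an assumed arm of 20 to 40 patients, missed positives number n × p × f:

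- p = 2%: 20 × 0.02 × 0.25 = 0.1 up to 40 × 0.02 × 0.75 = 0.6.
- p = 5%: 20 × 0.05 × 0.25 = 0.25 up to 40 × 0.05 × 0.75 = 1.5.

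These figures only restate their inputs. They show that a rare event gives a small absolute loss.

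**Step 5. Is the difference explained?**

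A note lets the sponsor reduce or stop PK and ADA sampling as data emerge. It stands under A13-7, A14-7, A14-9 and A16-7 alike, so it cannot account for a difference in what is planned. No other reason appears in these appendices.

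**The case against.** The case for leaving the schedule alone has four parts.

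**Much of the PK comparison survives.** All three Cohort 1 schedules share the Cycle 1 pre-dose sample, the Cycle 1 post-infusion sample and the Cycle 2 trough. A reader might infer that the 600 mg versus 2100 mg comparison is lost altogether for tiragolumab. The documents do not support that. Cycle 1 peak and trough can still be compared, and only exposure after dose 2 and around surgery cannot.

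**Cohort 2 covers later time points.** A14-9 plans up to six post-baseline tiragolumab ADA samples with RO7247669 at 2100 mg. This softens the consequence. It does not close the gap, because Cohort 2 is a different population, sampled only while on treatment and not at discontinuation.

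**The loss may be trivial.** Tiragolumab ADA is called rare, and under-counting requires some conversions after day 22. A reader might infer that incidence in this arm will certainly come out lower. The schedules support only that it can be equal or lower. The existing evidence comes from tiragolumab alone or with atezolizumab, so it says little about co-administration with RO7247669.

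**The harm depends on main-body text.** The immunogenicity objective, the ADA-evaluable definition and any planned cross-arm ADA table lie outside the appendices checked here. That stands as a limit on the consequence, but it does not change the schedules.

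**Conclusion.** The inconsistency is real and unexplained in the appendices. As written, A14-7 gives one post-baseline tiragolumab ADA sample per patient against four in A16-7 and five in A13-7, and no tiragolumab measurement after the final dose. Two consequences follow:

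- Tiragolumab ADA incidence in the 2100 mg + Tira arm of Cohort 1 can be under-counted and is not comparable with the other tiragolumab arms unless all are restricted to Cycle 2 Day 1.
- Tiragolumab exposure after dose 2 and around surgery cannot be compared with the 600 mg + Tira arm.

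RO7247669 ADA is unaffected, since A14-7 samples it up to 6 months after surgery. The size of any under-count cannot be derived and may be small. The conclusion assumes that ADA will be summarised by arm from the planned samples.

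A reader might also infer that A16-7 is deficient for lacking the 6-month tiragolumab sample in A13-7. That is a matter of preference, because A16-7 already follows patients to Week 13. The point bears on interpretability, not on the validity of the trial.

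**What to change.** Add tiragolumab PK and ADA to A14-7 at Weeks 7, 10 and 13, to match A16-7, and to the discontinuation visit in A14-9. Serum is already drawn for RO7247669 at each of these visits, so no new visit is needed.

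For patients already past these visits, limit any cross-arm tiragolumab ADA comparison to the common Cycle 2 Day 1 sample and say so in the table title. Testing retained serum is not proposed, because the appendices do not show that enough is kept or that consent covers it.

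If the shorter schedule is intended, state the reason in A14-7 and apply the same restriction to every patient in the arm.

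The cost is one table edit in each of the two schedules, the extra assays and possibly slightly more serum per existing draw.
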